14.5 Safety Analysis

The cumulative incidence of adverse events observed during the procedure and throughout the follow-up period, will be presented in tabular format. A detailed list of all adverse events will be presented. The

	Title: Evaluation of EndoZip™ System (AS) in Obese Patients who failed to reduce weight with non-surgical weight-loss methods		
Document No: CL00003	Rev: 1.0	Page:	55 of 83

adverse event rate will be compiled with respect to seriousness, severity, expectedness and relationship to procedure and device. In addition, listings of all safety measures will be produced.

14.6 Secondary Endpoints Analysis

Excess Weight Loss % (EWL%)

EWL% of patients at 1, 2, 6 and 12 month(s) by study group will be summarized with descriptive statistics with 95% confidence intervals.

The percent excess weight loss (%EWL) will be calculated as $(\text{Weight(BL)} - \text{Weight(Visit)}) / \text{ExcessWeight(BL)}$, where ExcessWeight(BL) is calculated as difference between the patient's baseline weight in kilograms and the kilograms at which the patient's BMI would be 25.

Change of Weight and Waist Circumference Over 12 Months from Baseline

Change from baseline in BMI at 1, 2, 6 and 12 month(s) by study group will be summarized with descriptive statistics with 95% confidence intervals.

Changes in Weight-related Quality of Life (IWQOL) Questionnaire at 12 months

IWQOL questionnaire records will be summarized by study groups will be summarized with descriptive statistics with 95% confidence intervals.

Time analysis

Time analysis including procedure duration, anesthesia duration, patient recovery duration will be evaluated and will be summarized with descriptive statistics with 95% confidence intervals.

Change in Comorbid Conditions

Clinically significant changes at 6 and 12 months in fasting plasma glucose and HbA1c concentrations, change in systolic and diastolic blood pressure, changes in plasma total cholesterol, low-density lipoprotein cholesterol and triglyceride concentrations, will be evaluated and will be summarized with descriptive statistics with 95% confidence intervals

Percentage of patients who had clinically significant change will be provided with 95% confidence interval.

Usability and Physicians' satisfaction

Physicians' satisfaction will be evaluated by a questionnaire will be summarized with descriptive statistics with 95% confidence intervals.

	Title: Evaluation of EndoZip™ System (AS) in Obese Patients who failed to reduce weight with non-surgical weight-loss methods		
Document No: CL00003	Rev: 1.0	Page:	56 of 83

The physicians will be asked to fill-in a dedicated questionnaire to include their feedback on the procedure.

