	
The overall significance level for this study is 5%, confidence intervals will be two-sided using a 95% confidence level, except for treatment by site interaction that will be tested at a significance level of 10%.
 
Primary Endpoints
 
The %TBWL at each visit will be calculated as $100 * (\text{Weight(BL)} - \text{Weight(Visit)}) / \text{Weight(BL)}$, where weight is measured in kilograms. %TBWL will be summarized with descriptive statistics at each follow-up visit.
 
%TBWL will be evaluated by using repeated measures analysis of covariance (ANCOVA MIXED model). Baseline weight, center and visit will be used as covariates. Baseline weight will be entered as a continuous variable so that the potential for collinearity problems will be minimized.
 
The unstructured covariance matrix structure will be used. If the model doesn't converge, then either the compound symmetry or autoregressive (whichever model has the lower AIC statistic) covariance matrix structure will be used instead. For this evaluation, no imputation of missing data is considered beyond the model estimates.
 
The model estimated mean %TBWL at each visit will be presented with 95% confidence interval and level of significance.
 
A count and percentage of patients achieving at least 5% TBWL will be presented with exact 95% confidence interval.
 
Subset Analysis of the primary endpoint:
 
Additionally, the %TBWL median, mean and standard deviation and percent of patients with greater than 5%TBWL will be summarized. Covariates may include demographic data (sex, age, BMI) or other baseline characteristics.
 
Secondary Endpoints
 
Excess Weight Loss % (EWL%)
 
EWL% of patients at 1, 2, 6 and 12 month(s) by study group will be summarized with descriptive statistics with 95% confidence intervals.
 
The percent excess weight loss (%EWL) will be calculated as $(\text{Weight(BL)} - \text{Weight(Visit)}) / \text{ExcessWeight(BL)}$, where ExcessWeight(BL) is calculated as difference

--	--

	
Title: Evaluation of EndoZip™ System (AS) in Obese Patients who failed to reduce weight with non-surgical weight-loss methods
	
Document No: CL00003	Rev: 1.0	Page: 19 of 83

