14.4 Primary Endpoint Analysis

The %TBWL at each visit will be calculated as $100 * (\text{Weight(BL)} - \text{Weight(Visit)}) / \text{Weight(BL)}$, where weight is measured in kilograms. %TBWL will be summarized with descriptive statistics at each follow-up visit.

%TBWL will be evaluated by using repeated measures analysis of covariance (ANCOVA MIXED model). Baseline weight, center and visit will be used as covariates. Baseline weight will be entered as a continuous variable so that the potential for co-linearity problems will be minimized.

The unstructured covariance matrix structure will be used. If the model doesn't converge, then either the compound symmetry or autoregressive (whichever model has the lower AIC statistic) covariance matrix structure will be used instead. For this evaluation no imputation of missing data is considered beyond the model estimates.

The model estimated mean %TBWL at each visit will be presented with 95% confidence interval and level of significance.

A count and percentage of patients achieving at least 5% TBWL will be presented with exact 95% confidence interval.

14.4.1 Subset Analysis of the primary endpoint:

Additionally, the %TBWL median, mean and standard deviation and percent of patients with greater than 5%TBWL will be summarized. Covariates may include demographic data (sex, age, BMI) or other baseline characteristics.

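### The 12-month %EWL has no model and no missing-data rule, so it would run too high if patients who lose little weight leave more often

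*Combined protocol and SAP*

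**What the plan says.** Section 14.4 (Primary Endpoint Analysis) treats total body weight loss in two ways. It plans a table: "TBWL will be summarized with descriptive statistics at each follow-up visit". It also plans a model: "TBWL will be evaluated by using repeated measures analysis of covariance (ANCOVA MIXED model", with baseline weight, center and visit as covariates. The missing-data sentence belongs to that model: "For this evaluation no imputation of missing data is considered beyond the model estimates".

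Section 14.6 (Secondary Endpoints Analysis) treats excess weight loss in one way: "EWL% of patients at 1, 2, 6 and 12 month(s) by study group will be summarized with descriptive statistics with 95% confidence intervals". Excess weight is the "difference between the patient's baseline weight in kilograms and the kilograms at which the patient's BMI would be 25". The BMI change, which stands under the weight and waist heading, is handled in the same descriptive way. Neither has a model or a rule for absent weights. The synopsis (section 3.0) repeats these texts.

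Section 14.2.1 makes the mFA set principal for primary and secondary efficacy endpoints. One follow-up visit is enough to meet its visit condition, so a patient without a 12-month weight can belong to it. The sentence in section 14.2.2 on several measurements per patient concerns correlation, not absent visits.

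The %TBWL formula multiplies by 100. The %EWL formula, introduced in both places by "The percent excess weight loss (%EWL) will be calculated as", does not.

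**The concern.** A descriptive mean with a confidence interval and no missing-data rule is, in practice, a summary of the patients weighed at that visit. At 12 months those are the patients who stayed. A patient who lost little by month 6 and then left still contributes to the 12-month %TBWL through the model, but not to the 12-month %EWL.

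The protocol contains routes by which leaving could be related to weight loss. Section 11.3 allows withdrawal for noncompliance with procedures or visits, and when an exclusion criterion appears. One exclusion criterion (number 22 in section 11.2) is taking medication that causes weight loss, which a patient with a poor result might start. None of this shows that selective dropout will happen. If it does, a listed secondary endpoint would look better than it should, with no model-based estimate beside it.

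**Working it through.** **1. The formulas on the plan's own figures.** The plan gives no expected %EWL, dropout rate or power calculation. The nearest figures are the earlier study's 6-month results in section 6.3: mean weight 111.1 kg, mean height 174 cm, loss 17.8 kg, %TBWL 16.2, %EBWL 54.3.

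- %TBWL = 100 × 17.8 / 111.1 = 16.0 (reported 16.2).
- Excess weight = 111.1 − 25 × 1.74² = 111.1 − 75.69 = 35.41 kg.
- %EWL as written = 17.8 / 35.41 = 0.503; multiplied by 100 it is 50.3 (reported 54.3).

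The reported value is on the percent scale, so the written formula lacks the factor 100. The gap between 50.3 and 54.3 is no sign of error: one is a ratio of means and the other a mean of patient ratios, and the earlier study's definition of excess weight is not given.

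**2. How the two measures relate.** With both on the percent scale, %EWL = k × %TBWL, where k = BMI / (BMI − 25) at baseline. At BMI 30, k = 30/5 = 6.0; at BMI 40, k = 40/15 = 2.7. A small bias in weight loss therefore becomes a larger number of %EWL points.

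**3. Size of the bias.** Large-sample simulation, 200,000 patients per scenario.

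- *From the documents:* 6-month %TBWL mean 16.2, SD 6.0; BMI range 30 to 40.
- *Assumed:* 12-month mean 16.2, SD 7; 1- and 2-month means 7 and 10, SDs 3 and 4; adjacent-visit correlation 0.7 or 0.9; uniform BMI; dropout after month 6 of 10%, 20% or 30%; logit slope 1 or 2 per SD of weight loss.
- *Model estimate:* regress 12-month %EWL on the 1-, 2- and 6-month values among those observed, predict for everyone, and average.

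Dropout depending on the 6-month loss already seen:

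| Dropout | True mean | Observed patients | Excess | Model |
|---|---|---|---|---|
| 10% | 60.7–60.8 | 62.4–64.1 | 1.7–3.3 | 60.6–60.8 |
| 20% | 60.6–60.8 | 63.7–67.0 | 3.1–6.2 | 60.3–60.9 |
| 30% | 60.6–60.7 | 65.4–69.3 | 4.7–8.7 | 60.1–60.7 |

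Dropout depending on the unseen 12-month loss:

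| Dropout | Observed patients, excess | Model, excess |
|---|---|---|
| 10% | 2.3–3.9 | 0.5–2.0 |
| 20% | 4.5–7.0 | 1.0–3.6 |
| 30% | 6.6–9.9 | 1.4–5.1 |

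With dropout unrelated to weight loss, the observed mean is within 0.1 of the truth.

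A simulation at trial size gives the same picture. It used n = 39 (45 less two run-in patients at each of three sites), about 24% missing, a true mean near 56 and dropout depending on the last observed loss. The observed-case excess was 2.3, 4.4 and 5.6 points from weak to strong dependence, and the model was within 0.1.

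**4. Why baseline BMI belongs in the %EWL model.** In the first table the model falls short by up to 0.6 (60.7 − 60.1), at correlation 0.7. There, 12-month %TBWL regresses on 6-month %TBWL with slope 0.7 × 7/6 = 0.817 and intercept 16.2 × (1 − 0.817) = 2.97. Multiplying through by k gives %EWL at 12 months = 2.97k + 0.817 × %EWL at 6 months. The term in k depends on BMI, and a model without BMI omits it. At correlation 0.9 the intercept is 16.2 × (1 − 1.05) = −0.8, so little is lost.

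**The case against.** **Descriptive summaries are legitimate here.** The trial is a pilot, its analyses are mainly descriptive, its sample size has no statistical basis, and no %EWL test or threshold is set. This stands, and it makes the point an improvement rather than a defect that undermines the trial.

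**The plan has a partial safeguard.** Because %TBWL is both tabulated and modelled, a gap between the two would hint at selective dropout. In the scenarios of the first table, the observed %TBWL is 16.7 to 18.5 against a modelled 16.2. This also stands, but it gives the reader no corrected %EWL.

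**Dropout may be low.** All eleven patients in the earlier study reached 6 months, and this protocol plans monthly contact by visit or phone. The documents give no dropout rate, so the bias could be negligible.

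**The bias is modest against sampling error.** With the earlier study's 6-month SD of 28.4 and about 30 patients weighed (39 × 0.76), the 95% half-width is 2.045 × 28.4 / √30 = 10.6 points. An excess of 2.3 to 5.6 is about a fifth to a half of that. Still, a shift in a known direction is not covered by the interval.

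**The model is no cure.** The second table shows up to 5.1 points of remaining bias at 30% dropout. The simulation gives the model only three earlier weights. The trial also weighs patients at 1 week and at 4, 8 and 10 months, which would help for patients who leave late.

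**Observed cases is inferred from silence.** True: section 14.6 does not use the term. No other rule is given, and a plain mean leaves no other reading.

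The responder co-primary in section 14.4 also has no missing-data rule. That is a separate matter.

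**Conclusion.** The point holds in a limited form. The 12-month %EWL, as planned, describes only the patients weighed then. Under dropout tied to 6-month loss it is too high by about 2 to 9 points for 10% to 30% dropout; under dropout unrelated to weight loss it is unbiased. The size rests on assumed dropout rates, dependence and visit correlations.

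A reader might infer more than the documents support:

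- *That %EWL will be overstated.* Nothing shows that selective dropout will occur.
- *That %EWL and %TBWL will give conflicting answers.* They differ by BMI/(BMI − 25) and weight patients differently, so their means are not expected to match even with complete data.
- *That the missing factor 100 distorts the result.* It changes the scale only, and the label and the earlier study's values make the intent plain.
- *That the modelled %TBWL is safe in any case.* That holds only if dropout depends on observed weights.

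**What to change.** In section 14.6 and the synopsis:

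1. Estimate %EWL and the other weight-derived changes at 6 and 12 months with the same type of repeated-measures model as %TBWL. For %EWL add baseline BMI as a covariate.
2. Keep the observed-case table and show the number weighed at each visit.
3. State that the model estimate assumes dropout depends only on observed weights, and that otherwise it reduces the bias without removing it.
4. As a separate editorial correction, write the formula in both places as 100 × (Weight(BL) − Weight(Visit)) / ExcessWeight(BL).

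The cost is plan wording and slightly more analysis; no new data are needed. The reported %EWL may look slightly less favourable.

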14.7 Interim Analyses

An interim analysis is planned after enrollment of 25 patients undergone at least 2 months of follow up aims to verify the recruitment pace and patients' adherence to the study flow.

15.0 Adverse Events (AEs) and Complications

AE and AE subcategories are defined per ISO14155:2020, as described below.

15.1 Adverse Event (AE)

An AE is any untoward medical occurrence, unintended disease or injury, or untoward clinical signs (including abnormal laboratory findings) in patients, user or other person, whether or not related to the investigational medical device and whether anticipated or unanticipated.

This definition includes events related to the investigational medical device or the comparator and the procedures involved. For users or other persons, this definition is restricted to events related to the use of investigational medical devices or comparators.

AEs will be collected starting from the time patient is enrolled until the follow-up period is completed.

15.2 Serious Adverse Event (SAE)

A Serious AE (SAE) is an AE that led to any of the following

- a) Death,
- b) Serious deterioration in the health of the patient, users, or other persons as defined by one or more of the following:
 - 1) A life-threatening illness or injury, or
 - 2) A permanent impairment of a body structure or a body function including chronic disease, or
 - 3) In-patient or prolonged hospitalization, or
 - 4) Medical or surgical intervention to prevent life-threatening illness or injury or permanent impairment to a body structure or a body function,

NOTE: Planned hospitalization for a pre-existing condition, or a procedure required by the clinical

	Title: Evaluation of EndoZip™ System (AS) in Obese Patients who failed to reduce weight with non-surgical weight-loss methods		
Document No: CL00003	Rev: 1.0	Page:	57 of 83

investigational plan, without serious deterioration in health, is not considered a SAE.

15.3 Serious Health Threat

Some important medical events, although they may not result in death, be life-threatening, or require hospitalization may still be considered SAEs. Life threatening means that the patient, users or other persons, was at imminent risk of death or a serious deterioration in the health, and that requires prompt remedial action, medical or surgical intervention, for other patients, users or other persons to prevent one of the outcomes listed above.

This would include events that are of significant and unexpected nature such that they become alarming as a potential serious health hazard or possibility of multiple deaths occurring at short intervals.

15.4 Adverse Device Effect (ADE)

An Adverse Device Effect (ADE) is an AE related to the use of an investigational medical device.

This definition includes AEs resulting from insufficient or inadequate instructions for use, deployment, implantation, installation, or operation, or any malfunction of the investigational medical device.

This definition includes any event resulting from use error or from intentional misuse of the investigational medical device.

15.5 Serious Adverse Device Effect (SADE)

A Serious Adverse Device Effect is an adverse device effect that has resulted in any of the consequences characteristic of an SAE.

15.6 Unanticipated Serious Adverse Device Effect (USADE)

An Unanticipated Serious Adverse Device Effect is a serious adverse device effect which by its nature, incidence, severity, or outcome has not been identified in the current risk assessment.

15.7 Adverse Event Severity Classification

Mild	Awareness of event, but easily tolerated
Moderate	Discomfort enough to cause some interference with activities of daily living (ADL); Minimal local or noninvasive intervention indicated.

	Title: Evaluation of EndoZip™ System (AS) in Obese Patients who failed to reduce weight with non-surgical weight-loss methods	
	Document No: CL00003	Rev: 1.0

Severe	Hospitalization or prolongation of hospitalization indicated; disabling; limiting self-care ADL*
--------	--

Severity will be defined according to the following criteria:

NOTE: An AE can be classified as severe and not deemed a SAE. Similarly, a SAE is not automatically severe in nature.

* Self-care ADL refer to bathing, dressing and undressing, feeding self, using the toilet, taking medications, and not bedridden.

15.8 Adverse Event Relationship Classification

Relationship to study product administration will be determined as follows:

- *No Relationship:* No relationship between the AE and the administration of study treatment and a known relationship to other etiologies such as concomitant medications, procedure, or patient's clinical state.
- *Possible Relationship:* An AE that follows a reasonable temporal sequence from administration of the study treatment and follows a known response pattern to the study treatment but could have been produced by the participant's clinical state or by other therapies.
- *Probable Relationship:* An AE that follows a reasonable temporal sequence from administration of the study treatment; follows a known response pattern to the study treatment; and cannot be reasonably explained by the known characteristics of the participant's clinical state or by other therapies.
- *Definite Relationship:* An AE that follows a plausible temporal sequence from administration of the study treatment and follows a known response pattern to the study treatment. The reaction cannot be reasonably explained by the known characteristics of the patient's clinical state or other modes of therapy administered to the patient.
- *Unknown/Impossible to Determine:* Given the information available, sequence and timing of events, it is unknown or impossible to determine the relationship of the AE with the study treatment.

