Safety evaluation - There were no adverse events related to the study. Two events unrelated to the device and / or EndoZip procedure occurred during the study.

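### In 15.8 the Possible, Probable and Definite grades all require a known response pattern, so a device effect new in nature can only be graded Unknown

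*Combined protocol and SAP*

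**What the plan says.** Section 15.8 introduces one five-level scale: "Relationship to study product administration will be determined as follows". Possible is "An AE that follows a reasonable temporal sequence from administration of the study treatment and follows a known response pattern to the study treatment". That grade also supposes that the patient's own condition or another treatment might explain the event. Probable and Definite repeat the timing and known-pattern conditions and add that no other reasonable explanation exists. No Relationship needs "a known relationship to other etiologies such as concomitant medications, procedure" or the patient's clinical state. The last grade applies when, on the information available, "it is unknown or impossible to determine the relationship of the AE with the study treatment". Section 15.8 does not say what makes a pattern known.

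The device-effect definitions contain no such condition. Section 15.4 covers any AE related to use of the device, including those from faulty instructions "or any malfunction of the investigational medical device". Section 15.6 covers a serious device effect "which by its nature, incidence, severity, or outcome has not been identified in the current risk assessment".

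The grades feed the reporting. Section 9.1 characterises safety by AE and SAE incidence according to relation to study treatment. Section 14.5 compiles AE rates by relationship to procedure and to device, and also promises a list of every AE. Section 15.12 sets the minimum AE record, which includes relatedness to the EndoZip system, the study procedure, or both.

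**The concern.** A relatedness scale should be able to record that an investigator believes the device caused an event not described before. In 15.8 recognisability is a precondition of every positive grade. An investigator who sees a new kind of event, well timed after the procedure and with no rival cause, has no grade that expresses that judgement. Unknown is what remains, and it misdescribes a case in which the investigator does hold a view on cause.

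This matters because 5.1.3 names long-term safety as an aim, and experience with the device is thin. The completed EndoZip study in 6.3 had 11 patients followed for 6 months with an earlier configuration, and reported that "There were no adverse events related to the study". Its extension adds one technical failure (6.3.1). Follow-up here is 12 months, so the completed study supplies no pattern for effects that first appear in the second half of the year.

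A smaller mismatch lies alongside. The scale has one object, the study product, and names procedure among the other causes that support No Relationship. Section 14.5 wants procedure and device both tabulated.

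**Working it through.** The check is of definitions, and the plan gives no figure to reproduce. Take two test events, both with plausible timing and no known response pattern. Event A has no other explanation. Event B has another conceivable cause that is not established.

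| Grade in 15.8 | What it demands | Event A | Event B |
|---|---|---|---|
| No Relationship | established other cause | fails | fails |
| Possible | timing, known pattern, other cause conceivable | fails on pattern and on other cause | fails on pattern |
| Probable | timing, known pattern, no reasonable other explanation | fails on pattern | fails on pattern and on explanation |
| Definite | as Probable, with slightly different timing wording | fails on pattern | fails on pattern and on explanation |
| Unknown | relationship cannot be determined | only grade left | only grade left |

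For event B, Unknown is defensible. For event A it is not: the investigator's view is that the device caused it.

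Set against 15.4, event A is a device effect if related, and no known pattern is asked for. Set against 15.6, event A, if serious, is what the word nature provides for. An effect unanticipated only in incidence, severity or outcome could still follow a known pattern, so the gap is confined to effects new in nature.

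Next, the repair. If the pattern condition is removed from Possible only, event A still fails Possible, which expects another conceivable cause, and still fails Probable on pattern. If it is removed from Possible and Probable, event A becomes Probable and event B becomes Possible. Both grades therefore need the edit.

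On object of rating: 15.8 has one (study product), 14.5 has two (procedure, device), and 15.12 mentions both without requiring two ratings or giving a procedure scale.

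On size: the exact two-sided 95% upper limit for 0 related AEs in 11 patients is 1 − 0.025^(1/11) = 28.5%. An event type with an assumed true incidence of 5% per patient would be missed in all 11 with probability 0.95^11 = 57%. These figures show how little EndoZip-specific experience exists. They do not measure the defect, because an event unseen in 11 patients may still follow a pattern known from elsewhere. For scale only, moving one patient between related and not related changes a per-patient rate by 1/45 = 2.2 percentage points at the maximum planned enrolment.

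**The case against.** The strongest reply is that little depends on the grade. All AEs are recorded whatever their relatedness (15.11, 15.12), and SAEs go to the sponsor without a relatedness filter. Under 15.12 the sponsor forwards all AE records to the DSMB, which makes its own written judgement of relationship to the device, and nothing binds it to the wording of 15.8. Section 7.2 expects complications like those of other endoscopic suturing devices and lists them in broad classes, so few events may be truly without a known pattern. All of this stands and limits the consequence. It does not remove the gap: the documents give the DSMB no alternative criteria, and 15.8 does not say that borrowed patterns count as known.

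Several stronger readings are tempting and should not be drawn:

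- **That 15.8 bars adverse device effect or USADE status.** No section ties that status to a grade.
- **That related events will be hidden.** Unknown is its own grade. No section pools it with No Relationship or drops it from a table, and every AE is listed.
- **That procedure relatedness is not collected.** Section 15.12 already asks for it. What is missing is a clear requirement for two ratings.
- **That the 2- and 6-month endoscopies must have their own relatedness column.** In 14.5, procedure can naturally be read as the EndoZip procedure itself.
- **That follow-up of events turns on the grade.** Section 15.11 extends monitoring for device-related events, but 15.12 and the footnote to the schedule in 13.10 state other rules, so this holds only if 15.11 governs.

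A fair point against the repair is that the sutures are non-absorbable (6.1) and follow-up lasts 12 months, so timing alone discriminates weakly. Without the pattern condition some incidental AEs could become Possible. That cost is real and cannot be quantified from the documents.

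**Conclusion.** The point holds as a defect of wording. Read literally, 15.8 leaves Unknown as the only grade for a device effect that is new in nature, plausibly timed and without another cause, and this is inconsistent with 15.4 and 15.6. The consequence is that such events would be shown as Unknown rather than related in the 9.1 and 14.5 summaries. How often this would occur cannot be estimated: it depends on what raters accept as known and on how many effects are new in kind, and the documents give neither. The DSMB review, the full listing and borrowed patterns keep the likely effect small.

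The conclusion assumes that investigators apply the grades as written. If they use judgement instead, the problem becomes inconsistent grading between sites. The device and procedure mismatch is a harmonisation matter, secondary to this.

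**What to change.** In 15.8, remove the known response pattern as a necessary condition from both Possible and Probable. Keep it as a supporting criterion, or reserve it for Definite, which would also separate Definite from Probable more clearly than the present text does.

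For harmonisation, state that each AE is rated on the scale twice, once for the device and once for the study procedure, so that 15.8 supplies what 14.5 tabulates and 15.12 already points to. In No Relationship, specify that the procedure meant is a non-study procedure.

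The cost is an edit to two grades, a clarifying word in a third, and a second relationship field if the eCRF lacks one, which the documents do not say. Some incidental AEs may move from Unknown to Possible, so reported related-event rates may rise. Showing Unknown as its own row in the tables would let readers see that shift. No visit or sample size changes.
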